## 11.7 CT Assessment

CT scans will be performed preoperatively in all patients at UK sites.

#### 11.7.1 Cohort 1A and Cohort 1B

In Cohort 1A and 1B, 0.5 to 1.0mm tantalum markers will be applied in the bone (9 in the acetabulum and 9 in the proximal femur) in order to be able to measure possible acetabular or femoral component migration in relation to those markers on ultralow dose postoperative CT scans [42]. These ultralow-dose CT scans will be performed postoperatively at a several time points, for different reasons as explained in Table 3. All CT scans will be done over short exposure length (20cm) to include acetabulum and proximal femur. Information is summarised in Table 11. The measurement of migration from the CT shall be carried out with a validated computational migration analysis protocol. Validation reports are available on request.

#### Table 11. Schedule of CT scans

CT Scan	Time	Tube current (mA)	Energy (mSv)	Reason for scan	Cohort(s)
1	Pre-op	100	1.5	Hip alignment	All UK
2	2-3 days	20	0.31	Implant migration time zero	1A and 1B
3	6 weeks	20	0.31	Implant migration	1A and 1B
4	3 months	20	0.31	Implant migration	1A and 1B
5	6 months	100	1.5	Bone ongrowth & Implant migration	1A
6	6 months	20	0.31	Implant migration	1B
7	9 months	20	0.31	Implant migration	1B
8	12 months	20	0.31	Implant migration	1A and 1B
9	24 months	20	0.31	Implant migration	1A and 1B

#### 11.7.2 Radiation Dose

#### Cohort 1A

These patients will receive a total of 5 AP pelvis exposures and 5 lateral hip exposures. They will also undergo 2 low dose CT scans and 5 ultra low dose CT scans. This results in a total effective dose of approximately 8.5mSv.

#### Cohort 1B

These patients will receive a total of 5 AP pelvis exposures and 5 lateral hip exposures. They will also undergo 1 low dose CT scan and 7 ultra low dose CT scans. This results in a total effective dose of approximately 7.6mSv.

#### Cohort 2

These patients will receive a total of 8 AP pelvis exposures and 8 lateral hip exposures. If at a UK site then they will additionally undergo 1 low dose CT scan. This results in a total effective dose of approximately 8mSv.

#### **Bilateral cases**

Some patients will receive bilateral hip replacements and due to the timings of their procedures (relative to the study time points) they may be in one cohort for one hip but the other cohort for the second hip. Where patients are undergoing bilateral procedures unnecessary duplication of scans will be avoided by using existing images from the other procedures wherever possible.

#### **DEXA scans**

Some patients (in all cohorts) will additionally receive one DEXA scan. The dose and risk from the DEXA scan (~10 $\mu$ SV) is several orders of magnitude smaller than the dose and risk from the other imaging components. It adds an additional risk of fatal cancer of approximately 1 in 2 million.

#### Maximum dose

The maximum possible dose in this study will be for staggered bilateral patients who were in cohort 1A for their first procedure and cohort 2 for their second. As a consequence of avoiding duplicate imaging, this group will receive two low dose CT scans, 5 ultra low dose CT scans, 13 AP Pelvis exposures, 13 lateral hip exposures and a potentially an additional DEXA scan. A dose constraint of 15mSv is therefore proposed for this study.

An effective dose of 15 mSv has an associated cumulative lifetime risk of fatal cancer induction of approximately 1 in 1300, using a nominal risk coefficient for cancer in the adult population of 5% per Sievert (ICRP Publication 103). For comparison, the natural incidence rate for cancer in the UK is approximately 1 in 2.5 (CRUK 2010).

Regardless of the cohort or combination of cohorts that the participants are involved in, the majority (approximately 75%), of the radiation dose that they will receive is additional to standard of care in the UK.

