#### 8.2.3 Cohort 1B Only

#### **CT** Assessment

Cohort 1B (46 patients) will undergo a low dose CT scan preoperatively and an ultra-low dose CT scan at the following time points: immediately postoperatively (2days), 6 weeks, 3 months, 6 months, 9 months, 1 year and 2 years. This will be used to evaluate the interfaces between implants and bone to assess possible migration of the acetabular and femoral components based on tantalum markers.

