#### Table 8. Schedule of procedures: Staggered bilateral patients recruited from Cohort 1B into Cohort 2 or vice versa

Col	hort 1B Study Hip	Pre-op	Op day	2D	6 wks	3 mos	6 mos	9 mos					1 year		2 years		3 years			4 years	5 years		6 years	7 years		8,9 years	10 years	
Col	hort 2 Study Hip								Pre-op	Op day	2D	6 wks		6 mos		1 year		2 year	3 year			5 years			7 years			10 years
	Informed consent								~																			
	Inclusions/exclusions								~																			
	Patient registration								~																			
	DXA Scan								√^ ≤12 mos prior																			
	Medical History								 																			
	Operative data									 																		
L	Treadmill gait								 				✓			 					✓	 						
Assessment	Harris Hip Score	Ass	essm	nents	don	e as r	oer Ta	able	 			 	~	 	✓	 	✓	 	√		✓	 		~	 		✓	 
sess	Oxford Hip score				3				 			 	~	 	✓	 	✓	 	 	✓	✓	 	~	~	 	~	✓	 
As	Imperial Hip Score								 			 	~	 	✓	 	✓	 	 	✓	✓	 	~	~	 	~	~	 
	EQ-5D								√			 	~	 	✓	 	✓	 	 	✓	✓	 	~	~	 	~	✓	 
	AP & lateral Radiographs								√ ≤12 mos prior		~	 				 	✓	~	 		~	 					✓	~
	Low dose CT scan								⊻ ≤12 mos prior																			
	Ultra low dose CT												~		✓													
	Conmed questions								~	√	√	√	~	√	~	 	✓	 	√	✓	✓	√	~	✓	√	✓	✓	 
	Record Adverse Event(s)								 	 	~	 	~	 	~	 	✓	~	 	~	~	 	~	~	~	~	~	~

 $\checkmark$  = Cohort 1B Study Hip  $\checkmark$  = Cohort 2 Study Hip  $\checkmark$  = To be taken only if previously DXA scan not done

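### The 15 mSv dose constraint is set from the Cohort 1A then 2 route, but the Cohort 1B/2 route as scheduled is 0.62 mSv higher, at about 15.4 mSv

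*Protocol*

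**What the plan says.** Protocol Section 11.7.2, under Maximum dose, says: "The maximum possible dose in this study will be for staggered bilateral patients who were in cohort 1A for their first procedure", with Cohort 2 for the second. It counts 2 low-dose CTs, 5 ultra-low-dose CTs, 13 AP and 13 lateral exposures for them, attributes that count to avoiding duplicate imaging, and concludes: "A dose constraint of 15mSv is therefore proposed for this study". Under Bilateral cases the same section gives the general rule that "unnecessary duplication of scans will be avoided by using existing images from the other procedures wherever possible".

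For Cohort 1B, Section 11.7.2 states: "They will also undergo 1 low dose CT scan and 7 ultra low dose CT scans". Section 8.2.3 agrees: "Cohort 1B (46 patients) will undergo a low dose CT scan preoperatively and an ultra-low dose CT scan at the following time points", followed by seven time points.

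Table 8 is headed "Staggered bilateral patients recruited from Cohort 1B into Cohort 2 or vice versa". It ticks a pre-operative low-dose CT for the Cohort 2 hip, to be taken within 12 months before. Its DXA row carries the condition "To be taken only if previously DXA scan not done"; its low-dose CT row does not. Table 6 (Cohort 1A then Cohort 2) has no low-dose CT row for the second hip. In Table 11 the 6-month low-dose scan, with the reason "Bone ongrowth & Implant migration", belongs to Cohort 1A only.

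**The concern.** The route named as the maximum is counted with image reuse. The schedule for another permitted route is written without it. The two low-dose CTs on the named route are Cohort 1A's own pre-operative and 6-month scans, so nothing is added for the second hip. On the Cohort 1B/2 route the two are the Cohort 1B pre-operative scan and the Cohort 2 pre-operative scan, and Cohort 1B also has two more ultra-low-dose scans than Cohort 1A.

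A dose constraint should hold for anyone imaged exactly to schedule. If it is set from a route that is not the highest as scheduled, a patient can exceed it with no protocol deviation, and the radiation reviewer has been given the wrong worst case.

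**Working it through.** **Inputs.** Low-dose CT 1.5 mSv and ultra-low-dose CT 0.31 mSv (Table 11). Cohort totals from Section 11.7.2: 1A 8.5 mSv with 5 radiograph pairs; 1B 7.6 mSv with 5 pairs; UK Cohort 2 8 mSv with 8 pairs. A pair is one AP and one lateral exposure. The DXA dose (about 0.01 mSv) is negligible and is left out.

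**Radiograph dose.** The protocol does not state it, so I infer it as (total − CT dose) / pairs:

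- Cohort 1A: (8.5 − 2×1.5 − 5×0.31) / 5 = 0.790 mSv per pair
- Cohort 1B: (7.6 − 1.5 − 7×0.31) / 5 = 0.786
- Cohort 2: (8.0 − 1.5) / 8 = 0.8125, from a total given only to the nearest whole mSv

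Taking the totals as rounded (8.45–8.55, 7.55–7.65, 7.5–8.5), the values consistent with all three run from 0.780 to 0.796. I use 0.79.

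**The plan's own figure.** From the stated totals, 8.5 + 8.0 − 1.5 (second-hip CT not taken) = 15.0 mSv. From components, 2×1.5 + 5×0.31 + 13×0.79 = 14.82 mSv. The 15 mSv figure is reproduced.

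**Each route.** Dose = 1.5 × low + 0.31 × ultra-low + 0.79 × pairs. Ranges use 0.780 to 0.796.

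| Route | Low | Ultra-low | Pairs | mSv (range) |
|---|---|---|---|---|
| 1A then 2, as stated | 2 | 5 | 13 | 14.82 (14.69–14.90) |
| 1B/2, as in Tables 3 and 8 | 2 | 7 | 13 | 15.44 (15.31–15.52) |
| 1B/2, second low-dose CT avoided | 1 | 7 | 13 | 13.94 (13.81–14.02) |
| 2 then 2, UK, no images reused | 2 | 0 | 16 | 15.64 (15.48–15.74) |
| 2 then 2, UK, CT reused | 1 | 0 | 16 | 14.14 (13.98–14.24) |

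Rows 1 and 2 differ by 2 × 0.31 = 0.62 mSv whatever the radiograph dose. At Cohort 2's 0.8125 per pair they become 15.11 and 15.73. From the stated totals alone, 1B/2 is 7.6 + 8.0 = 15.6 mSv. It stays within 15 mSv only below (15 − 3.0 − 2.17) / 13 = 0.756 mSv per pair, which is outside the implied range.

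The 2 then 2 rows are a caution only. They use the stated 8 pairs per hip, Table 7 was poorly legible in the text available to me, and shared AP pelvis films would lower them.

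**Same rule on every route.** With CT reuse throughout, 1A then 2 is 14.82 and 1B/2 is 13.94. With no reuse, 1A then 2 gains a third low-dose CT and is 14.82 + 1.5 = 16.32, against 15.44. Either way 1A then 2 stays above 1B/2. The order reverses only because the text and Table 6 drop the second CT while Table 8 keeps it.

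**Risk at 5% per Sv.** 1 / (0.015 × 0.05) = 1 in 1333; 1 / (0.01544 × 0.05) = 1 in 1295. Both are about 1 in 1300.

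**The case against.** The strongest reply is that the reuse rule covers all bilateral patients, including those whose hips fall in different cohorts. Applied to Cohort 1B/2, it gives 13.9 mSv and the named maximum is right for this pair of routes. The Table 8 tick allows a scan up to 12 months old, so an existing CT can satisfy it. The rule speaks of existing images, which could include ultra-low-dose scans. Table 5 gives simultaneous bilateral patients a single CT, so one scan can serve both hips.

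That makes reuse plausible but does not guarantee it:

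- The rule applies only where reuse is possible, whereas the text claims a maximum possible dose.
- Cohort 1B has no 6-month low-dose scan to fall back on. Table 8 places the Cohort 2 pre-operative visit after the Cohort 1B hip's 9-month visit, and the Cohort 1B pre-operative scan may predate surgery by up to 4 months. It can therefore be about 9 to 13 months old, or more, against a 12-month window. Shorter gaps are allowed (Section 9.4 permits the second hip from 6 months), so some patients could reuse the scan and others could not.
- Nothing says whether an ultra-low-dose scan is an acceptable substitute for the pre-operative one.

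A second reply is that the excess over 15 mSv rests on an inferred radiograph dose and on no radiograph being shared; one avoided pair would bring 15.44 down to 14.65 mSv. That is fair as to the total. But the plan's own count for the named route also shares no radiographs, so the comparison is like for like, and the 0.62 mSv difference does not depend on the radiograph dose.

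**Conclusion.** The point holds, as a minor one. As scheduled, Cohort 1A then 2 is not the highest-dose route: Cohort 1B/2 is 0.62 mSv above it, at about 15.4 mSv (15.3 to 15.5), or 15.6 mSv from the stated totals. Against 15 mSv that is 0.44/15 = 2.9% to 0.6/15 = 4% over. The 0.62 mSv rests only on stated CT doses and counts. Exceeding 15 mSv also needs the inferred radiograph dose, no shared radiographs, and a second low-dose CT actually taken.

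The practical effect is small. It concerns staggered bilateral patients only, within a cap of 25 on all bilateral patients (Section 9.2.2), and no endpoint or analysis is affected. I do not claim that Cohort 1B/2 is the overall maximum; a UK Cohort 2 then 2 patient with no images reused could be slightly higher. The error is that the text and the tables apply different reuse rules to a stated safety limit.

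**What to change.** Choose one of two:

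- **Make the scan conditional.** In Tables 7 and 8, mark the second-hip low-dose CT as needed only if no usable CT exists, as is already done for DXA. Define usable (maximum age, and whether an ultra-low-dose scan qualifies). Then confirm that the worst remaining case, including patients for whom reuse is not possible, is within 15 mSv.
- **Keep the scans as scheduled.** Name the correct maximum route in Section 11.7.2 and restate the maximum and the constraint, at about 16 mSv on these figures, with the radiation reviewer.

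The first costs a footnote in two tables and a short check. The second costs an amended paragraph and a notification to the radiation reviewer. The choice belongs to the sponsor and its radiation experts.

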## 11.8 Toxicology

Metal ion testing (whole blood Co, Cr and Ti concentrations) will be performed in Cohort 1A and 1B preoperatively and at 3, 6, 12 and 24 months postoperatively.

#### 11.8.1 Analytical methodology

All metal ion measurements will be performed at a laboratory with experience in metal ion measurements (the Trace Element Laboratory in the Department of Clinical Biochemistry at Charing Cross hospital – [name]) using high resolution, inductive-coupled plasma mass spectrometry (Element 2 HR-ICP-MS, Thermo Scientific, Waltham, MA, USA). A minimum quantification limit should be 0.5  $\mu$ g/l with a reproducibility of 95%. The analyses should be controlled using IQC and where possible EQA (Quebec Multi-element External Quality Assessment Scheme and/or UK National External Quality Assessment Scheme for Trace Elements).

#### 11.8.2 Sample Sources

For the assessment of metal ion levels in patients with a MoM hip prosthesis various matrices, such as whole blood, serum, urine and hip fluid are used. Analyses in whole blood or serum are preferable, since the metal ion concentration in urine samples are variable and depend on the hydration of the patient. Twenty-four hour urine concentrations are more reliable but a 24-hour urine collection is cumbersome and often incomplete. In this study whole blood samples will be used, as there is no need for centrifugation after the blood is drawn and the samples can thus be stored at the participating sites for up to 1 week in the refrigerator at 4°C. Temperature is to be recorded in the Temperature Log with a validated thermometer.

#### 11.8.3 Collection Techniques

One of the major technical challenges of biological metal ion testing is the risk for contamination from needles, collection tubes or containers and thus rigorous protocols are advocated for every step of the process.

#### 11.8.4 Collection tubes

For whole blood, Becton-Dickinson (BD) Trace Elements K2EDTA tubes 368381 are recommended. The blood can be shipped as such, without centrifugation for the analysis of whole blood.

To minimise the risk of contamination unopened trace metal rated collection tubes must be used.

#### 11.8.5 Sample volume needed for metal ion analysis

2 ml of whole blood is sufficient for analysis.

#### 11.8.6 Sample Collection Procedures

A blood sample of 2 ml will be collected for each patient in a K2EDTA collection tube.

#### 11.8.7 Protocol for blood sampling

It is preferable to use a non-metal needle but a metal needle can also be used provided the first 5ml of blood are discarded in order to eliminate the metal ions from the needle. If a venflon is placed to draw the blood, the needle is removed and the first 5ml of blood are thrown away in order to eliminate the metal ions from the venflon needle. If a vacutainer or a butterfly needle is used to draw the blood, the first 5ml of blood must be discarded before the K2EDTA 2.0 ml is collected for the metal ion analysis.

#### 11.8.8 Labelling K2EDTA collection tube

Tubes and labels will be provided by the co-ordinating centre. Please complete the following information on for each collection tube:

Subject number: Date of visit: Time point: Site:

# **11.8.9** Stability of the blood samples and transportation or shipping recommendations

Metals are rather stable in whole blood and shipping at room temperature is allowed if it takes less than 3 days.

The samples can be stored at 4°C for up to one week before shipping them.

The samples can be stored frozen (- 20°C) for months.

#### 11.8.10 Blood Sample Shipping Procedures

Each centre will be responsible for organising the courier shipment of all samples. Each shipment must be accompanied by a sample manifest form, provided by the co-ordinating centre.

The samples may be kept refrigerated at 4°C if shipped within 14 days. Otherwise they need to be frozen at -20 °C.

The blood samples must be shipped to:

Trace Element Lab Charing Cross Hospital FAO: [name] [name] United Kingdom [contact], [contact]

The courier will ensure the samples are shipped to arrive Monday to Friday only, and must ensure that wherever possible samples are transported to arrive between the hours of 09:00 and 16:00. Please remember to notify the recipient as soon as possible, but at least two working days in advance of any shipment.

#### 11.9 Lost to Follow-up

Some actively enrolled subjects will not return for their follow-up visits due to a variety of reasons. The investigator/study site must use every reasonable measure to obtain follow-up clinical data: phone calls, regular mail and e-mail, certified letters to urge subjects to return for clinic follow-up or ascertain if a patient has moved, died, or otherwise become lost to follow-up. Reasons for loss to follow-up will be recorded if known.

## 11.10 Documentation of Study Completion Status

The completion status of the patient (e.g. completed per protocol, withdrawal, device removed, death, lost-to-follow-up, or other reason) should be recorded on the withdrawal/off study case report form.

# 12 Monitoring plan

#### 12.1 Source data

[figure not shown]
Investigators are responsible for obtaining and maintaining complete subject health information in the medical record for each patient (source documents). Examples of source documents are e.g., hospital records, clinic and office charts, memoranda, dispensing records, patient questionnaires, clinic evaluation transcriptions, operative notes, radiographs, radiology reports, blood collection and shipment records, research subject files, etc. As a minimum entry, the principal investigator shall ensure that clinical records are clearly marked to indicate that the patient is enrolled in a particular clinical investigation.

#### 12.2 Direct access

The investigator will provide direct access to source data/documents to permit possible study-related monitoring, audits, Ethics Committee review, and regulatory inspections. This study can be monitored by the study manager or a qualified person designated by the chief investigator. During these visits, the monitor will check for completion of the entries on the case report forms, their compliance with the study protocol and will compare the CRF entries with the source data. In addition, the monitor will determine whether all adverse events have been appropriately reported within the time periods required. The investigator will also provide Sponsor, Sponsor's agents, IRB/IEC and regulatory agencies with direct access to all source data/documents to permit Study-related monitoring, audits, IRB/IEC review, and regulatory inspections if requested.

#### 12.3 Data handling and record keeping requirements

Case report forms (CRFs) will be supplied by the Co-ordinating centre (Imperial College London). Patients will be identified by patient identification number as recorded in the subject identification log. Only the investigator will have the key to identify individual patients. The clinical investigator is responsible for the timely and accurate completion of CRFs as per ICH-GCP guidelines.

(CRFs) at the time of the scheduled visits and transcribed to the online electronic data capturing (EDC) platform, Castor. All data should be transcribed and uploaded to the online EDC within 2 weeks of the scheduled visit.

If the investigator relocates, retires, or for any reason withdraws from the study, the chief investigator and the Sponsor (Embody Orthopaedic Limited) should be prospectively notified. The study records must be transferred to an acceptable designee.

## 12.4 Participating centre day-to-day monitoring

Day-to-day monitoring should be carried out by those responsible for the running of the study at each participating site. This would normally include the following checks:

- Data collected are consistent with the protocol
- The case report forms (CRFs) are only being completed by authorised staff
- No key data are missing
- A review of recruitment rates, withdrawal and losses to follow-up
- All queries and validation alerts generated when data is transcribed to the EDC platform are resolved

## 12.5 Central monitoring

The investigation manager will be responsible for centralised monitoring, which can indicate problems, and can be used to efficiently direct monitoring activities to those sites requiring further investigation and/or additional training support.

Central monitoring of data will be used to assess the following:

- Unusual patterns or trends
- Issues with plausibility or consistency
- Safety signals
- Other deviation from the protocol/trial requirements such as poor/late completion of CRFs.

#### 12.6 Risk-based monitoring

A Risk Based Monitoring (RBM) approach will be used, which will focus on triggered monitoring visits to identify potential issues. RBM will focus on risk assessments highlighted as part of the study that will have high potential impact to patient safety and data quality. However, the co-ordinating centre retains the rights to increase on-site monitoring in case of issues or problems and if deemed necessary.

## 12.7 Monitoring report

The principal investigator will be provided with a monitoring report including action items.

# 13 Data management

#### 13.1 Data Submission

Sites will be required to enter trial data into Castor's electronic case report forms (eCRF). Trial data should be entered into the appropriate eCRF within one week of each scheduled visit. Images will be anonymised and sent to the coordinating site in a secure format. All AEs and SAEs should be reported as per Section 16. Blood toxicology reports will be obtained from Imperial Healthcare NHS Laboratory. The coordinating centre will keep a log of all eCRFs, scans and reports received throughout the investigation.

#### 13.2 Quality Control

Data validation will be performed on the data collected. Data validation checks for missing or incomplete information. This is carried out in two ways:

- 1. **Field validations** are encoded in the eCRFs to warn users of incomplete or incorrect information. These checks are performed automatically on each field as data is entered into the field.
- Source data verification will be performed on a sample of completed forms. eCRF forms will be compared to the original paper form entries to ensure data has been entered correctly. This will be undertaken by the lead coordinating site.

If any inconsistencies are found, a "query" will be raised with the PI at the site in question. Records of all queries raised will be maintained. Corrective actions will also be documented, including the timeframe of response.

All stored CRFs will be kept in a secure environment such as a locked filing cabinet in a locked room at each participating centre.

